## 7 Visit Schedule and assessments

The Flow Chart (synopsis) lists assessments and indicates with an “X” the visits during which they are performed. Patients should be seen for all visits at the designated time-point or as close to it as possible. A time window for the visits of up to +/- three weeks will be allowed.

All data obtained from the assessments listed in the Flow-Chart and described in detail in the subsections below must be supported in the patient’s source documentation.

The study visit schedule consists of screening period for up to 8 weeks prior to the initiation of therapy followed by an open treatment period until final height is reached. The study plan timetable (please refer to the Flow Chart Treatment Period) indicates the number and timing of the planned visits. During these visits, the mentioned efficacy and safety parameters will be assessed. It is important to maintain the visit schedule during the treatment period as accurately as possible. If any individual visit date does not conform to the planned schedule, the subsequent visit should be realigned to maintain the schedule relative to the start of the treatment period.

The clinical and laboratory investigational plan per visit is summarized in the Flow Chart Treatment Period.

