#### **7.4.7 Adverse events**

The investigator has the responsibility for managing the safety of individual subject and identifying adverse events.

An adverse event (AE) is any untoward medical occurrence (e.g., any unfavorable and unintended sign, including abnormal laboratory findings, symptom or disease) in a subject after providing written informed consent for participation in the study until the end of study visit. Therefore, an AE may or may not be temporally or causally associated with the use of a investigational medicinal product.

In addition, all reports of intentional misuse and abuse of the product are also considered an adverse event irrespective if a clinical event has occurred.

The occurrence of adverse events should be sought by non-directive questioning of the subject at each visit during the study. Adverse events also may be identified when they are volunteered by the subject during or between visits or through physical examination, laboratory test, or other assessments.

Abnormal laboratory values or test results constitute adverse events only if they fulfill at least one of the following criteria:

- they induce clinical signs or symptoms,
- the investigator considers them to be clinically relevant,
- they require therapy.

Clinically relevant abnormal laboratory values or test results should be identified through a review of values outside of normal ranges/clinically notable ranges, relevant changes from baseline or the previous visit, or values which are considered to be non-typical in subject with underlying disease.

Adverse events must be recorded on the adverse events CRF with the following information within 10 days of learning of its occurrence (if the event is serious (refer to Section 7.4.8) it must be recorded in the CRF within 24 hours of learning of its occurrence):

- the severity grade (indicating most severe grade during the course of the adverse event)
  - mild: usually transient in nature and generally not interfering with normal activities
  - moderate: sufficiently discomforting to interfere with normal activities
  - severe: prevents normal activities
- its relationship to the study drug(s) (suspected/not suspected)
  - Not suspected: The temporal relationship of the clinical event to trial drug administration makes a causal relationship unlikely, or other drugs, therapeutic interventions or underlying conditions provide a sufficient explanation for the observed event.

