  - Suspected: The temporal relationship of the clinical event to trial drug administration makes a causal relationship possible, and other drugs, therapeutic interventions or underlying conditions do not provide a sufficient explanation for the observed event.
  - If the event is due to lack of efficacy or progression of underlying illness (i.e. progression of the study indication) the assessment of causality will usually be 'Not suspected'. The rationale for this guidance is as follows:
    - the symptoms of a lack of efficacy or progression of underlying illness are not caused by the trial drug, they happen in spite of its administration
    - both lack of efficacy and progression of underlying disease can only be evaluated meaningfully by an analysis of cohorts, not on a single subject
- its duration (start and end dates) or 'ongoing' at the 30 day safety follow-up /end of study visit
- whether it constitutes a serious adverse event (SAE) (see Section 7.4.8 for the definition of SAE)

**Unlike routine safety assessments, SAEs are monitored continuously and have special reporting requirements; see Section 8.1**

- action taken: All adverse events must be treated appropriately. Treatment may include one or more of the following: no action taken (i.e. further observation only); study drug dosage adjusted/temporarily interrupted; study drug permanently discontinued due to this adverse event; concomitant medication given; non-drug therapy given, subject hospitalized/subject's hospitalization prolonged.
- Its outcome (not recovered/not resolved; recovered/resolved; recovering/resolving, recovered/resolved with sequelae; fatal; or unknown)

Once an adverse event is identified, it must be followed until its resolution or until it is judged to be permanent, and assessment must be made at each visit (or more frequently, if necessary) of any changes in severity, the suspected relationship to the study drug, the interventions required to treat it, and the outcome.

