#### **7.4.8 Serious adverse events**

A SAE is defined as any adverse event (appearance of (or worsening of any pre-existing) undesirable sign(s), symptom(s) or medical conditions(s) which meets any one of the following criteria:

- is fatal or life-threatening
- results in persistent or significant disability/incapacity
- constitutes a congenital anomaly/birth defect
- requires inpatient hospitalization or prolongation of existing hospitalization, unless hospitalization is for:
  - routine treatment or monitoring of the studied indication, not associated with any deterioration in condition (specify what this includes)
  - elective or pre-planned treatment for a pre-existing condition that is unrelated to the indication under study and has not worsened since the start of study drug
  - treatment on an emergency outpatient basis for an event not fulfilling any of the definitions of a SAE given above and not resulting in hospital admission
  - social reasons and respite care in the absence of any deterioration in the subject's general condition

- is medically significant, i.e. defined as an event that jeopardizes the subject or may require medical or surgical intervention to prevent one of the outcomes listed above

Death without known medical event must always be reported as SAE.

Life-threatening in the context of a SAE refers to a reaction in which the subject was at risk of death at the time of the reaction; it does not refer to a reaction that hypothetically might have caused death if more severe.

All malignant neoplasms will be assessed as serious under “medically significant” if other seriousness criteria are not met.

Medical and scientific judgment must be exercised in deciding whether other situations should be considered serious AEs, such as important medical events that might not be immediately life threatening or result in death or hospitalization but might jeopardize the subject or might require intervention to prevent one of the other outcomes listed above. Examples of such events are intensive treatment in an emergency room or at home for allergic bronchospasm, blood dyscrasias or convulsions that do not result in hospitalization or development of drug dependency or abuse.

Any suspected transmission of an infectious agent via a medicinal product is also considered a serious adverse event.

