##### **4.6.2.1 Adverse events**

Adverse events (AEs) are to be recorded during the whole study period.

AEs are coded according to Novartis MedDRA, Version 24.1.

The AE data will be listed, sorted by site code, patient number, and preferred term. This list will include: adverse event, MedDRA system organ class, MedDRA preferred term, start date, stop date, intensity, outcome, relationship to study drug, action taken, and a variable indicating whether an AE was considered a serious adverse event (SAE).

AEs starting prior to start of treatment will not be included in the summary tables, but listed only.

A general summary table of AEs will contain the total number of AEs, the total number of SAEs, and separate descriptions of the splits for the variables relationship to study drug, action taken,

outcome and intensity. Outcome is categorized according to the CRF as “resolved” (i.e. resolved completely or resolved with sequelae), “ongoing”, “fatal” or “unknown”.

The incidence of an AE is defined as the number of patients who experience that event, divided by the number of patients in the SAF population. With AE incidence, each event will be counted only once for a given patient. More specifically, if a patient reports the same event more than once, as determined by preferred term and system organ class, that patient will be counted only once for the incidence of the AE. For example, when a patient reported three instances of headache, this patient counts only once towards the total incidence of headache. Incidence of events within a system organ class is defined similarly. Whenever incidence is cross-tabulated with intensity in the summary tables, the incidence of an AE will be calculated for each level of intensity, i.e., the number of patients who experience that AE on a certain level of intensity.

Incidence tables will provide information about rates of AEs per patient-year, calculated as  $\{(number\ of\ patients\ who\ experience\ that\ event)\ / (years\ of\ exposure)\}$ . Additional tables will enable a direct comparison of formulation specific rates of events per patient year.

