**FIGURE 14.2-2.21 Mean IGF-1 SDS serum levels over time, means  $\pm$  95% CI (FAS)**

**FIGURE 14.2-2.22 Mean IGFBP-3 SDS serum levels over time, means  $\pm$  95% CI (FAS)**

**5.4 Safety Tables including shells**

**TABLE 14.3-1.1 GENERAL SUMMARY OF ADVERSE EVENTS (SAF)**

		Number of patients (%) (N=277)	Number of adverse events (%)
Any adverse events	XXX	(XX.X%)	XXX
Relationship to study drug			(XX.X%)
Not suspected	XXX	(XX.X%)	XXX
Suspected	XXX	(XX.X%)	XXX
Missing	XXX	(XX.X%)	XXX
Intensity			(XX.X%)
Mild	XXX	(XX.X%)	XXX
Moderate	XXX	(XX.X%)	XXX
Severe	XXX	(XX.X%)	XXX
Missing	XXX	(XX.X%)	XXX
Serious adverse event			(XX.X%)
No	XXX	(XX.X%)	XXX
Yes	XXX	(XX.X%)	XXX
Missing	XXX	(XX.X%)	XXX
Outcome			(XX.X%)
Resolved	XXX	(XX.X%)	XXX
Ongoing	XXX	(XX.X%)	XXX
Missing	XXX	(XX.X%)	XXX
Action taken			(XX.X%)
Nothing	XXX	(XX.X%)	XXX
Study drug dosage adjusted/temporarily interrupted	XXX	(XX.X%)	XXX
Study drug permanently discontinued due to this AE	XXX	(XX.X%)	XXX
Concomitant medication given	XXX	(XX.X%)	XXX
Non-drug therapy given	XXX	(XX.X%)	XXX
Hospitalization/prolonged hospitalization	XXX	(XX.X%)	XXX
Missing	XXX	(XX.X%)	XXX

No AEs (including SAEs) that started prior to start of treatment are included.

**TABLE 14.3-1.2 INCIDENCE OF ADVERSE EVENTS BY SYSTEM ORGAN CLASS, PREFERRED TERM, AND INTENSITY, ALL ADVERSE EVENTS (SAF)****TABLE 14.3-1.2.1 INCIDENCE OF ADVERSE EVENTS FOR OVERWEIGHT\* PATIENTS AT BASELINE BY SYSTEM ORGAN CLASS, PREFERRED TERM, AND INTENSITY, ALL ADVERSE EVENTS (SAF)**

Defined by international cut off points for BMI for overweight by sex and age at baseline. The cut-off point is defined by the percentile that passes through BMI at 25 kg/m^2 at age 18.. Programming note: Same table shell as Table 14.3-1.2 will be used.

**TABLE 14.3-1.3 INCIDENCE OF ADVERSE EVENTS BY SYSTEM ORGAN CLASS, PREFERRED TERM, AND INTENSITY, DRUG-RELATED ADVERSE EVENTS (SAF)****TABLE 14.3-1.4 INCIDENCE OF SERIOUS ADVERSE EVENTS BY SYSTEM ORGAN CLASS, PREFERRED TERM, AND INTENSITY (SAF)****TABLE 14.3-1.5 INCIDENCE OF DRUG-RELATED SERIOUS ADVERSE EVENTS BY SYSTEM ORGAN CLASS, PREFERRED TERM, AND INTENSITY (SAF)****TABLE 14.3-1.6 INCIDENCE OF NON-SERIOUS ADVERSE EVENTS BY SYSTEM ORGAN CLASS, PREFERRED TERM, AND INTENSITY (SAF)**

Novartis MedDRA version System Organ Class Preferred Term	Intensity				Total number of patients	Patients per patient years#
	Mild	Moderate	Severe	Missing		
Blood and lymphatic system disorders						

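### The AE tables exclude events by start date alone, so an AE that began before the first dose and worsened or became serious on treatment can be missing from every one of them

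*Protocol*

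**What the plan says.** **Collection.** Protocol 7.4.7 defines an AE as an untoward occurrence "in a subject after providing written informed consent for participation in the study until the end of study visit". Protocol section 7 describes a "screening period for up to 8 weeks prior to the initiation of therapy". An AE can therefore have an onset before the first dose.

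**The record.** The items that Protocol 7.4.7 asks for on the AE form include:
- severity: "the severity grade (indicating most severe grade during the course of the adverse event"
- dates: "its duration (start and end dates) or 'ongoing' at the 30 day safety follow-up /end of study visit"
- seriousness: "whether it constitutes a serious adverse event (SAE"

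The same section has the site follow an identified event until it resolves or is judged permanent, re-assessing severity, suspected relationship and outcome at each visit.

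**Serious events.** Protocol 7.4.8 defines an SAE as "any adverse event (appearance of (or worsening of any pre-existing) undesirable sign(s), symptom(s) or medical conditions(s" that meets a seriousness criterion. Section 8.1 treats progression of an SAE already reported as follow-up to that report.

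**Analysis.** SAP 4.6.2.1 says "AEs starting prior to start of treatment will not be included in the summary tables, but listed only". The footnote to Table 14.3-1.1 reads "No AEs (including SAEs) that started prior to start of treatment are included", and the other AE table shells repeat it.

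**The concern.** The SAP sorts AEs into tabulated and listed-only by onset date, while the protocol lets one record span the pre-dose and on-treatment periods. Suppose an event starts as mild in screening and becomes severe on treatment. Its record shows the severe grade and a pre-treatment start date. The start date removes the record from the tables, and the on-treatment change goes with it.

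The incidence and severity of AEs is a stated secondary objective (Protocol 3.2, SAP 2.2) of a single-arm post-marketing safety study. Leaving out on-treatment worsenings can only lower the tabulated counts, grades and patient-year rates. A treatment-emergent definition that covers onset or worsening after the first dose would keep them. Neither document contains one.

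**Working it through.** The plan states no figure to reproduce. The check traces one hypothetical event through the rules.

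**Step 1: can a pre-dose AE record exist?** Yes. AEs count from consent, and screening may last up to 8 weeks. The SAP also writes a rule for such records, so it expects them.

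**Step 2: what happens to the record if the event worsens after the first dose?** The items required in 7.4.7 are a single worst grade, one pair of start and end dates, and one seriousness flag. None of them dates a worsening or the point at which the event became serious. The site goes on following the same event, and nothing in 7.4.7 tells it to open a second record. The natural result is that the grade or flag changes and the start date does not. This one-record reading is inferred from these provisions together; the protocol does not state it in so many words.

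**Step 3: what does the SAP do with the record?** The start date is before treatment, so the record is excluded. The footnote stands under seven shells, which serve Tables 14.3-1.1 to 14.3-1.27 (27 tables) and 14.3-1.2.1 (1 table): 27 + 1 = 28. The event adds zero to incidence, occurrence, the splits by intensity, outcome and action taken, and the rates per patient-year.

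**Step 4: is there a clause that brings it back?** None was found in Protocol 7.4.7, 7.4.8, 8.1 or 10.4.4, or in SAP 4.6.2.1 or the shells.

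**Step 5: where can it still appear?** In Listings 16.2.5.1 to 16.2.5.6, for which no start-date exclusion is stated. Depending on its nature, it can also reach Tables 14.1-3 (discontinuation reasons), 14.1-6 (dose changes), 14.3-2.7 (carbohydrate shifts), 14.3-3.3 (physical examination) or 14.3-3.7 to 14.3-3.9 (diabetes, IGT, IFG). This can make the report disagree with itself: a patient who stopped because a pre-dose AE worsened can count under adverse event in Table 14.1-3 but not in the permanent-discontinuation row of Table 14.3-1.1.

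**Step 6: size.** The documents bound only the observation time. With the 277 patients in the Table 14.3-1.1 shell and the full 8 weeks (56 days) for each:

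277 × 56 / 365.25 = 42.5 patient-years, a maximum.

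A count needs an AE rate and a worsening fraction, and the documents give neither. Purely as an illustration, assume 1 to 3 AEs per patient-year and 2% to 10% worsening after the first dose:
- AEs starting before treatment: 42.5 × 1 = 42 to 42.5 × 3 = 127
- of these, worsening later: 42 × 0.02 = 0.8 to 127 × 0.10 = 12.7

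Relative to on-treatment AEs, with a constant AE rate and an assumed mean exposure of 3 to 8 years:
- lowest share: (56 / 365.25) × 0.02 / 8 = 0.04%
- highest share: (56 / 365.25) × 0.10 / 3 = 0.5%

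**The case against.** **The one-record rule is inferred.** The CRF completion instructions are not available here, and Protocol 7.4.8 counts the worsening of a pre-existing condition within the SAE definition. A site could enter such a worsening as a new SAE dated on treatment, and the tables would then include it. The follow-up rule in 8.1 concerns SAEs already reported, so it does not settle the case of a non-serious screening AE that later becomes serious. This stands. A reader might infer that every SAE of this kind is certain to be lost; the documents support only that it can be, depending on how the site recorded it.

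**Pre-dose capture may be thin.** The flow chart marks AE recording from Visit 01, and the Visit 00 procedures do not list it. This stands. It makes 42.5 patient-years an upper bound, and it is a reason not to read the illustration of about 1 to 13 events as an estimate.

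**The events are not hidden.** They stay in the listings and may reach other tables. This stands, so the gap is in the AE summary tables, not in all output.

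**Most excluded events are rightly excluded.** An AE that began before the first dose and never worsened does not belong in on-treatment tables. Pre-dose onset also tends to support a causality rating of not suspected, so any effect on drug-related counts is weaker. Both points stand. They support a narrower exclusion rule, not the present one.

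**Medical-history conditions.** A reader might infer that worsening of a long-standing condition is also lost, through its original onset date. Nothing in the documents says that such a worsening is entered with that date, so this is not claimed.

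**No comparator arm.** No between-group comparison is biased. That is correct, but the absolute rates are themselves the result of this study.

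**Conclusion.** The gap is real and narrow. SAP 4.6.2.1 and the table footnotes set an exclusion by start date with no exception. With the AE record described in Protocol 7.4.7, that exclusion can leave an on-treatment worsening, including one that became serious, out of all 28 AE summary tables. The conclusion rests on the inferred one-record reading and on the site not having entered the worsening as a separate event.

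The number of events is probably small and cannot be estimated from the documents; the ranges above depend wholly on assumed rates. The laboratory-based diabetes tables for the primary endpoint do not use this rule. The point is still worth correcting before the final tables are produced. The omission runs in one direction, it concerns a stated secondary objective, and SAEs are rare enough for a single missing case to matter.

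**What to change.** Change the SAP only. The last patient was enrolled on 29 April 2010 (Protocol, Study status), so a new data-entry rule in Protocol 7.4.7 would have no effect on pre-dose records.

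1. In SAP 4.6.2.1, define tabulated AEs as those that start, worsen in severity or become serious on or after the first dose. Change the footnotes of Tables 14.3-1.1 to 14.3-1.27 and 14.3-1.2.1 to match.
2. Identify existing cases among AEs with pre-treatment onset that were ongoing at first dose. Use SAE form dates and post-dose action taken and outcome, with a targeted query to source where the timing of a severity change is unclear.
3. Where timing cannot be resolved, show the events in a separate summary row or table.

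The cost is more than wording. The AE items required by the protocol do not date a worsening, so step 2 cannot be programmed from onset date and worst grade alone and needs some retrospective checking in a study run on paper CRFs. The set is closed and limited. If it proves empty, the tables do not change; otherwise AE counts rise slightly.

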#### **7.4.8 Serious adverse events**

A SAE is defined as any adverse event (appearance of (or worsening of any pre-existing) undesirable sign(s), symptom(s) or medical conditions(s) which meets any one of the following criteria:

- is fatal or life-threatening
- results in persistent or significant disability/incapacity
- constitutes a congenital anomaly/birth defect
- requires inpatient hospitalization or prolongation of existing hospitalization, unless hospitalization is for:
  - routine treatment or monitoring of the studied indication, not associated with any deterioration in condition (specify what this includes)
  - elective or pre-planned treatment for a pre-existing condition that is unrelated to the indication under study and has not worsened since the start of study drug
  - treatment on an emergency outpatient basis for an event not fulfilling any of the definitions of a SAE given above and not resulting in hospital admission
  - social reasons and respite care in the absence of any deterioration in the subject's general condition

- is medically significant, i.e. defined as an event that jeopardizes the subject or may require medical or surgical intervention to prevent one of the outcomes listed above

Death without known medical event must always be reported as SAE.

Life-threatening in the context of a SAE refers to a reaction in which the subject was at risk of death at the time of the reaction; it does not refer to a reaction that hypothetically might have caused death if more severe.

All malignant neoplasms will be assessed as serious under “medically significant” if other seriousness criteria are not met.

Medical and scientific judgment must be exercised in deciding whether other situations should be considered serious AEs, such as important medical events that might not be immediately life threatening or result in death or hospitalization but might jeopardize the subject or might require intervention to prevent one of the other outcomes listed above. Examples of such events are intensive treatment in an emergency room or at home for allergic bronchospasm, blood dyscrasias or convulsions that do not result in hospitalization or development of drug dependency or abuse.

Any suspected transmission of an infectious agent via a medicinal product is also considered a serious adverse event.

